7.1 Sample Size Consideration

Contralateral breast without disease will serve as the control. In a sample of 40 patients with unilateral disease, we expect 60% of the patients to show significantly altered expression of miRNAs in the diseased breast as compared to the breast without disease for the test to be of clinical relevance. Ideally a detectable difference would be the difference between a null hypothesis of 0% and an alternative of 60% or a second alternative of 35%. Since this study is the first of its kind, we will consider the test to be not clinically relevant if less than 35% of patients show significantly altered expression miRNA in the diseased breast as compared to the breast without disease.

Using a two sample z-test, type I error of 0.05, and a two-sided significance level, a sample size of 40 will have greater than 80% power to detect a difference between a null hypothesis of 35% and an alternative hypothesis of 60%.

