7.2 Statistical Methods

The primary analysis will be conducted to determine the presence and expression levels of 800 miRNA's among DCIS and invasive breast cancer patients. Based on the resulting profiles, we will determine whether or not its expression for each miRNA from the tumor side differs from that of the normal side.

We will interrogate 800 miRNAs. The vast majority will not be expressed in any sample. A minority will be measurable/detectable in some samples and a smaller minority will be detectable in all samples.

The presence of miRNA can be as follows:

- a. Present in tumor and absent in normal
- b. Present in normal and absent in tumor
- c. Present at high level in tumor and low level in normal
- d. Present at high level in normal side and low level in tumor.

Of these a and c are most important and relevant for our analysis. If even a single miRNA is absent in tumor and present in 30% of cancers or if there is at least one miRNA out of these 800 that is present at low levels in all "normals" and high levels in 30% of tumors that would be a "success". We will dichotomize to low and high levels of miRNA to calculate frequencies and the associated risk estimates and 95% confidence intervals. The comparison of proportions will be performed using two-sample z-tests.

CONFIDENTIAL

This material is the property of [name]. Do not disclose or use except as authorized in writing by the study sponsor

7.3 *Subject Population(s) for Analysis*

Patients diagnosed with DCIS or invasive breast cancer.

8 Safety and Adverse Events

8.1 *Definitions*

Adverse Event

An ***adverse event*** (AE) is any symptom, sign, illness or experience that develops or worsens in severity during the course of the study. Intercurrent illnesses or injuries should be regarded as adverse events. Abnormal results of diagnostic procedures are considered to be adverse events if the abnormality:

- results in study withdrawal
- is associated with a serious adverse event
- is associated with clinical signs or symptoms
- leads to additional treatment or to further diagnostic tests
- is considered by the investigator to be of clinical significance

Serious Adverse Event

Adverse events are classified as serious or non-serious. A ***serious adverse event*** is any AE that is:

- fatal
- life-threatening
- requires or prolongs hospital stay
- results in persistent or significant disability or incapacity
- a congenital anomaly or birth defect
- an important medical event

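### Sections 7.1 and 7.2 set two unreconciled marks for the tumor-versus-normal comparison; on its natural reading, the 7.1 mark can be met with no usable marker

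*Combined protocol and SAP*

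**What the plan says.** Section 7.1 (Sample Size Consideration) works with a share of patients. Its target is "we expect 60% of the patients to show significantly altered expression of miRNAs in the diseased breast" relative to the healthy side, and its floor is "we will consider the test to be not clinically relevant if less than 35% of patients show significantly altered expression miRNA in the diseased breast". The power claim is attached to this share: "Using a two sample z-test, type I error of 0.05, and a two-sided significance level", the plan states that "a sample size of 40 will have greater than 80% power to detect a difference between a null hypothesis of 35"% and an alternative of 60%. The section does not say which miRNA must be altered, in which direction, whether patients must share it, or what makes one patient significantly altered.

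Section 7.2 (Statistical Methods) works per miRNA. It describes the primary analysis as profiling the miRNAs and judging, for each one, whether the tumor side differs from the normal side: "We will interrogate 800 miRNAs". It lists four patterns: (a) tumor only, (b) normal only, (c) high in tumor and low in normal, (d) the reverse. It then says "Of these a and c are most important and relevant for our analysis". Its success sentence has two limbs. The first reads "If even a single miRNA is absent in tumor and present in 30% of cancers", which contradicts itself. The second is clear and asks for at least one miRNA "present at low levels in all 'normals' and high levels in 30% of tumors that would be a 'success".

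No section ranks the two marks. Section 3.2 gives the primary endpoint as feasible miR analysis, which neither mark measures. The Study Summary describes a further approach: comparison with a normative reference population, binomial tests, the Benjamini-Hochberg procedure and ranking by p-value.

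**The concern.** The two sections apply different thresholds (35% and 30%) to different quantities: a share of patients altered in some unspecified way, and the frequency of one shared, tumor-high miRNA. The power statement belongs to the first quantity, while the primary analysis is the second.

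Section 2 (Study Objectives) gives the eventual goal as a screening tool. That needs a marker that recurs across patients and is raised on the tumor side. A patient share with no shared-miRNA or direction requirement can be large without any such marker. With no ranking, the team could also choose between the two marks after seeing the data.

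**Working it through.** **Inputs.** N = 40 unilateral patients, floor 35%, target 60%, two-sided 0.05 (7.1). 800 miRNAs and a success mark of 30%, read here as at least 30% (7.2). Expected adequate bilateral NAF in 77% of participants (Section 2).

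**The plan's own figure: whose power is it?**
- Two-sample z-test as named, 40 per group, pooled proportion 0.475: [0.25 − 1.96·√(2·0.475·0.525/40)] / √((0.35·0.65 + 0.60·0.40)/40) = (0.25 − 0.2189)/0.1081 = 0.288, so power is 61.3%. The stated figure of over 80% is not reproduced.
- One-sample z-test of a patient share against a fixed 35%: [0.25 − 1.96·√(0.35·0.65/40)] / √(0.60·0.40/40) = (0.25 − 0.1478)/0.0775 = 1.319, so power is 90.6%. The stated figure holds.

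The mismatch with the named test is a separate matter. What counts here is that the claim makes sense as power for a single share of patients. It is not power for finding one miRNA among 800.

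**The marks side by side, as counts of 40**

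| | 7.1 | 7.2 (second limb) |
|---|---|---|
| Unit | patients | one miRNA across patients |
| Direction | not stated | high in tumor |
| Same miRNA | not stated | yes |
| Healthy sides | not stated | low in all |
| Mark | under 0.35 × 40 = 14 is irrelevant; target 0.60 × 40 = 24 | 0.30 × 40 = 12 is success |

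**7.1 met, 7.2 not met.** Read 7.1 as any miRNA in any direction.
- 24 patients, each tumor-high in a different miRNA: 24/40 = 60%, but the largest tumor-high count for any miRNA is 1/40 = 2.5%.
- A less extreme case has three miRNAs, each tumor-high in 8 different patients. Then 24/40 = 60% are altered, but each miRNA reaches only 8/40 = 20%, below 30%.

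**7.2 met, 7.1 not met.** Suppose one miRNA is low in all 40 normals and high in x tumors, and those x patients also count as altered under 7.1. Then x ≥ 12 is needed for success, and total altered patients must be at most 13. So either x = 12 with at most one other patient altered in any way, or x = 13 with none.
- If that miRNA's true share is 30% to 32.5%, P(X = 12 or 13) is about 26%. This ignores the condition on the other patients.
- Assume, for illustration, that each of the other 28 patients independently has a 10% chance of some other alteration. P(at most one) = 0.9²⁸ + 28·0.1·0.9²⁷ = 0.052 + 0.163 = 0.215. At 25% it is 0.75²⁸ + 28·0.25·0.75²⁷, or about 0.003.
- The condition is stricter at x = 13, so the joint chance is below 0.26 × 0.215, under 6%, in the 10% case and below 0.1% in the 25% case.
- With fewer evaluable pairs the window shrinks. At 0.77 × 40 ≈ 31 pairs, only 10/31 (32.3%) lies between the marks. At 8 pairs, the number analyzed without oxytocin, no count does (2/8 = 25%, 3/8 = 37.5%).

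**The case against.** Four objections deserve an answer.

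1. Section 7.1 never says any miRNA or either direction. That is correct: it is the natural reading of an unqualified phrase, not the text. The case of 7.1 met without a marker depends on it. The firm defect is that the patient-level event is undefined, and that omission is what leaves the reading open.

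2. A reader might infer that the same data will readily be both a success and not relevant. The documents do not support that as the main consequence. If every patient counted by 7.2 also counts in 7.1, the double verdict is confined to the narrow window above. It would widen only if significantly altered were stricter than the high/low cut, and the plan defines neither.

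3. A reader might also infer that the trial has no answer to its own question. That goes too far. The stated objective and primary endpoint are feasibility (Sections 2 and 3.2), Section 3.1 calls this a proof of concept, and no stopping or treatment decision depends on either mark.

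4. Success of a pilot and clinical relevance could be separate ideas. They could, but the plan draws no such distinction and does not say how the two findings would be read together.

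The first three limit the size of the point. None of the four reconciles the two sections.

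**Conclusion.** The point holds in a limited form. Sections 7.1 and 7.2 set unreconciled marks, 35% of patients and 30% for one miRNA, on different quantities, and the power claim is attached to the one that 7.2 does not make primary. The more important consequence is that 7.1's 60% can be reached while no miRNA is tumor-high in more than 2.5% of patients. This assumes that 7.1 counts any miRNA in any direction. The reverse conflict is limited to 12 or 13 of 40, with total altered patients at most 13. It assumes that patients who are low on the normal side and high on the tumor side count as altered. Both results rest on the clear second limb of the success sentence and on 40 evaluable pairs unless stated otherwise.

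This should be fixed before the marker data are read. It does not undermine the feasibility endpoint.

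**What to change.** - Keep one deciding rule for the marker comparison: pattern a or c in the same miRNA, or in a pre-named panel. Define when one patient counts as showing it.
- Use one threshold in both sections, for example 35%, which 7.1 already uses as its floor and null. Reword the contradictory first limb in 7.2 to match.
- Report the any-miRNA, any-direction share of patients as descriptive only.
- Do not carry the stated power over to the rule kept. The 35% versus 60% claim concerns a patient share, and choosing the best of 800 miRNAs behaves differently under the null. Either recompute power with allowance for that selection (the Study Summary already names the Benjamini-Hochberg procedure), or state that the existing claim applies only to the descriptive share.

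The cost is revised wording plus a power calculation if the first option is taken. No procedure changes. The downside is that a directional, same-miRNA count will be lower than the any-miRNA count, and the restated power will probably be less favorable.

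### Section 7.1 gives a 60% mark, a 35% floor and a test against 35%, and does not say which decides clinical relevance; results of 14 to 23 of 40 can be described either way

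*Combined protocol and SAP*

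**What the plan says.** Section 7.1 sets up a within-patient comparison: "Contralateral breast without disease will serve as the control". It then makes four statements about the proportion of patients whose diseased breast differs from the control breast.

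- Expected rate: "In a sample of 40 patients with unilateral disease, we expect 60% of the patients to show significantly altered expression of miRNAs", and the same sentence ties this figure to relevance with "for the test to be of clinical relevance".
- Ideal contrast: a null of 0% against 60%, with 35% named as a second possible alternative.
- Floor: "we will consider the test to be not clinically relevant if less than 35% of patients show significantly altered expression miRNA".
- Power: a two-sample z-test, two-sided at 0.05, for which 40 patients are said to give more than 80% power to "detect a difference between a null hypothesis of 35% and an alternative hypothesis of 60"%.

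Section 7.2 adds a different success criterion: it is enough that one of 800 miRNAs separates 30% of tumors from the normal side. Section 3.1 calls the study a proof of concept with no power presented, and Section 3.2 makes feasibility of miR analysis the primary endpoint.

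**The concern.** The same phrase, clinical relevance, is attached to 60% and to 35%, and 35% also serves as the null of the powered test and as an alternative to 0%. Section 7.1 does not say whether the marks apply to the observed or the true proportion, how a result between them is classified, or which statement governs the conclusion.

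The relevance conclusion is something this pilot will be quoted for. An observed 35% clears the floor, equals the null value, and falls well short of 60%. With several cutoffs on paper, the one that is used can be chosen after the data are seen.

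**Working it through.** **Inputs.** All are from Section 7.1 unless noted: n = 40; null p0 = 0.35; alternative p1 = 0.60; two-sided alpha 0.05. Section 2 expects bilateral NAF of adequate volume from 77% of participants; 0.77 × 40 = 30.8, taken as 31 evaluable pairs. Each patient is counted once, as altered or not altered.

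**Reproducing the power figure.**

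- One-sample z against a fixed 35%: SE0 = √(0.35 × 0.65/40) = 0.0754; SE1 = √(0.60 × 0.40/40) = 0.0775. Power = Φ[(0.25 − 1.96 × 0.0754)/0.0775] = Φ(1.32) = 90.6%.
- Exact binomial, upper tail at most 2.5%: reject at 21/40 or more. P(X ≥ 21 | 0.35) = 0.017 and P(X ≥ 21 | 0.60) = 0.870.
- Two-sample z as named, 40 per group: pooled p = 0.475; Φ[(0.25 − 1.96 × √(2 × 0.475 × 0.525/40))/√((0.2275 + 0.24)/40)] = Φ(0.0311/0.1081) = 61.3%. With 20 per group it is 34.9%; 80% would need 62 per group.

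The claim of more than 80% therefore reproduces only as a one-sample test of 40 patients against a fixed 35%. The two-sample test that the text names does not give it.

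**Cutoffs if each statement is applied to observed counts, n = 40.**

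| Criterion | Cutoff | P(met) at true 35% | P(met) at true 60% |
|---|---|---|---|
| Not below 35% | 14/40 | 0.559 | 0.9996 |
| Reject 35%, one-sample z | 20/40 (z = 0.15/0.0754 = 1.99) | 0.036 | 0.926 |
| Reject 35%, exact | 21/40 (52.5%) | 0.017 | 0.870 |
| Observed 60% | 24/40 | 0.001 | 0.568 |

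At 19/40 the one-sample z is 1.66, so 35% is not rejected. Results of 14 to 19 clear the floor without rejecting 35%. A result of 20 rejects by z but not by the exact test. Results of 21 to 23 reject by both but fall short of 60%.

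**How often this zone (14 to 23 of 40) would occur.** At a true 35%: 0.559 − 0.001 = 0.558. At a true 60%: 0.9996 − 0.568 = 0.43.

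**At the expected yield, n = 31.** The floor is 11/31, met with probability 0.545 at a true 35%. The exact test needs 17/31: upper tail 0.019, power 0.781. At 16/31 the upper tail is 0.042, above 0.025. With 30 pairs the exact test needs 17/30 and power is 0.715.

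**The case against.** The strongest defence is that 35% and 60% are true rates: an ordinary pair of a rate not worth pursuing and a rate hoped for. Read so, they agree with the powered test of 35% against 60%, and the expected 60% is just a planning value. That reading is available, and under it the two marks do not contradict each other. But Section 7.1 does not state it. The floor is worded as a judgment on what patients show, which invites applying it to the observed rate, and 35% is also named as an alternative to 0%. Even on the benign reading, no decision rule is written down.

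A reader might infer something stronger: that the plan promises a 5% error rate and delivers 56%. The documents do not support that. The floor says when the test is not relevant; it never says that 35% or more is a pass. The 0.05 belongs to the z-test and not to the floor. For a two-sided test the comparable upper tail is nominally 2.5%. The 56% describes only what would follow if the floor alone decided.

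It is also fair to say that this is a single-arm pilot whose primary endpoint (Section 3.2) is feasibility and whose secondary endpoint (Section 3.3) is sufficient NAF volume. The 35% and 60% marks govern neither, and this lowers the severity.

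**Conclusion.** The point holds as a missing decision rule. Applied to the data, Section 7.1 supports cutoffs of 14/40, 20/40 or 21/40, and 24/40, and results from 14 to 23 of 40 can be described either way. The extremes perform very differently: the floor alone would be met 56% of the time at a true 35%, while requiring an observed 60% would miss a true 60% about 43% of the time (1 − 0.568). Separately, the stated power fits a one-sample test and not the two-sample z-test that is named.

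This rests on one altered or not-altered result per patient and on the marks being applied to observed proportions, which the text permits but does not require. The figures for 31 pairs also assume that the 77% bilateral NAF yield expected in Section 2, for women at increased risk, carries over to these patients. The matter should be corrected but is below must-fix.

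**What to change.** In Section 7.1:

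- State one rule: the test is called clinically relevant only if the lower limit of the exact 95% confidence interval for the one-sample proportion of patients with altered expression exceeds 35%. That means at least 21/40 (interval 36.1% to 68.5%), or 17/31.
- Describe 60% only as the planning alternative, and delete the 0% null together with the use of 35% as an alternative to it.
- Replace the two-sample z-test with this one-sample test.
- Restate power as 87% with 40 evaluable pairs and about 78% with 31, giving the 77% yield as the assumption.

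In Section 7.2, label the single-miRNA 30% success criterion as separate and exploratory.

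The cost is wording only, with no change to enrolment or procedures. The downside is a stricter bar than the 35% floor, and power slightly under 80% at the expected yield. The sponsor could instead keep 35% as a floor and report the test separately, but would then still have to say how results between the two are classified.

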3.1 General Design

We propose a pilot proof of principle study to assess and compare the miR fingerprint (or profile) in NAF, serum, and tissue from patients undergoing a lumpectomy or mastectomy for in situ or invasive breast cancer. As this study is a proof of concept there is no power presented. Other than the collection of NAF, treatment will not vary from the standard of care. The collection of all specimen types will be completed within the regularly scheduled operative time period. The surgery will not be prolonged in any way for specimen collection. Forty patients (20 with DCIS, 20 with invasive breast cancer) will be entered into the study. A total of 5 patients will also undergo pharmacokinetic (PK) draws during the time of surgery to assess the baseline oxytocin level. All other subjects enrolled will be enrolled into the “non-PK” cohort. Patients receiving care at the Breast Surgery Department at Columbia who meet criteria will be offered participation in the study. Patients will answer a brief questionnaire preoperatively. At the time of surgery patients will undergo a blood draw as well as collection of NAF (via prior administration of intranasal oxytocin, gentle massage, aspirator, and breast pump from both breasts). The NAF and blood samples will be sent to the pathology lab for analysis of miR profile. At the completion of the case, the breast tissue will be sent to pathology per routine. Once in pathology, 5 paraffin-embedded slices will be created to evaluate for miR profile. Serum, NAF, and tissue will be analyzed for their miR profile.

Once total RNA is extracted from the biological samples it will be processed to fluorescently label the microRNAs species according to the V2-Human microRNA array (Agilent). MicroRNA profiling will be obtained and analyzed using the gene-spring software analysis package. First, expression and cluster analysis will be performed to identify the microRNA that are expressed in our samples and to classify them accordingly to their expression. Then, the predicted targets of the over/down-regulated microRNAs will be identified using target prediction bioinformatics tools (TargetScan, Miranda and Pictarvert). Finally, statistical studies between over/under-represented microRNAs will be performed.

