5.3 Method for Assigning Subjects to Treatment Groups

All subjects will receive the same treatment.

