All patients will undergo a blood draw as well as collection of NAF (via prior administration of intranasal oxytocin, gentle massage, aspirator, and breast pump from both breasts). All biological samples will be collected by a qualified clinician. The NAF and blood samples will be sent to the pathology lab for analysis of miR profile. At the completion of the case, the breast tissue will be sent to pathology per routine. Once in pathology, 5 paraffin-embedded slices will be created to evaluate for miR profile. Serum, NAF, and tissue will be analyzed for their miR profile.

CONFIDENTIAL

This material is the property of [name]. Do not disclose or use except as authorized in writing by the study sponsor

Five patients who are participating in the PK cohort of the trial will also undergo a PK blood draw at the time of surgery prior to oxytocin administration. This will be used to assess the baseline oxytocin level and will be done in conjunction with the pre-oxytocin blood draw to assess miR. These patients will have a second blood draw approximately 30 minutes after the administration of oxytocin to assess oxytocin levels in comparison to the baseline. All blood draws will be done by a qualified clinician.

Once total RNA is extracted from the biological samples it will be processed to fluorescently label the microRNAs species according to the V2-Human microRNA array (Agilent). MicroRNA profiling will be obtained and analyzed using the gene-spring software analysis package. First, expression and cluster analysis will be performed to identify the microRNA that are expressed in our samples and to classify them accordingly to their expression. Then, the predicted targets of the over/down-regulated microRNAs will be identified using target prediction bioinformatics tools (TargetScan, Miranda and Pictarvert). Finally, statistical studies between over/under-represented microRNAs will be performed.

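### Section 7.1 credits its power of over 80% at 40 patients to a two-sample z-test, which gives about 61% even with 40 per group; the hypothesis described is one-sample, and a one-sample test does support the claim

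*Combined protocol and SAP*

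**What the plan says.** Section 7.1 makes the contralateral breast the control and defines its outcome per patient: "In a sample of 40 patients with unilateral disease, we expect 60% of the patients to show significantly altered expression of miRNAs". The comparison is between each patient's tumor side and her other side. The section then sets a floor: "we will consider the test to be not clinically relevant if less than 35% of patients show significantly altered expression miRNA". The power statement first names the method and size: "Using a two sample z-test, type I error of 0.05, and a two-sided significance level, a sample size of 40". For that combination, the section goes on to claim that the study "will have greater than 80% power to detect a difference between a null hypothesis of 35% and an alternative hypothesis of 60" per cent. No formula, software or per-group count is given. An earlier sentence in the section also mentions an ideal contrast with a null of 0%, but the power claim is for 35% against 60%.

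The design has one cohort. Section 5.3 states "All subjects will receive the same treatment", and section 3.1 states "Forty patients (20 with DCIS, 20 with invasive breast cancer) will be entered into the study". Section 7.1 does not compare the two disease groups.

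Three other places bear on the test:
- Section 3.1 says "As this study is a proof of concept there is no power presented".
- The Study Summary names a binomial test, but sets it against a normative reference population.
- Section 7.2 again names two-sample z-tests for comparing proportions, and adds a separate success rule based on a single miRNA at 30% of tumors.

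**The concern.** A two-sample z-test compares rates in two independent groups. Section 7.1 has one rate to estimate. The contralateral breast has already been used to decide whether each patient counts as altered, so it cannot also serve as a second sample. The 35% is a relevance threshold, not a rate observed in anyone.

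This matters because section 7.1 is the only quantitative justification for 40 patients, and its power figure cannot be reproduced with the test it names. Someone following the section literally would have no second group to enter. The wrong label also hides what the power depends on, which is the number of patients with usable material from both sides. Section 7.1 does not mention this. NAF is the only specimen the protocol says is taken bilaterally ("gentle massage, aspirator, and breast pump from both breasts", sections 3.1 and 6.1), and low NAF yield is the reason section 2 gives for extending the study.

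**Working it through.** **Inputs (section 7.1).** p0 = 0.35, p1 = 0.60, difference 0.25, two-sided 0.05 (z = 1.960), sample size 40, stated power above 80%.

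**1. The test as named, read generously as 40 per group.** The mean rate is (0.35 + 0.60)/2 = 0.475.

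Pooled power = Φ{[0.25 − 1.960·√(2·0.475·0.525/40)] / √[(0.35·0.65 + 0.60·0.40)/40]}
= Φ{[0.25 − 1.960·0.1117]/0.1081} = Φ(0.288) = 0.613.

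Unpooled power = Φ(0.25/0.1081 − 1.960) = Φ(0.353) = 0.638.

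Other variants at 40 per group:

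| Variant | Power |
|---|---|
| Arcsine | 61.9% |
| Continuity-corrected | 52.3% |
| Exact enumeration of the z-test | 63.9% |
| One-sided, pooled | 73.0% |
| One-sided, unpooled | 74.8% |

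None reaches 80%, so the plan's figure is not reproduced.

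**2. Size the named test would need for 80% power.**
Pooled: n = [1.960·√0.49875 + 0.8416·√0.4675]²/0.25² = 3.840/0.0625 = 61.4, so 62 per group.
Unpooled: n = (1.960 + 0.8416)²·0.4675/0.0625 = 58.7, so 59 per group.

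**3. The test that fits the hypothesis: one proportion against 35%, n = 40.**
Normal approximation: Φ{[0.25 − 1.960·√(0.2275/40)] / √(0.24/40)} = Φ{[0.25 − 1.960·0.0754]/0.0775} = Φ(1.319) = 0.906.
Exact binomial with at most 0.025 per tail: reject upward at 21 or more of 40. The upper-tail error at 35% is 0.0173 and the power at 60% is 0.870.
Both satisfy the stated claim.

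**4. Size of the one-sample z-test at n = 40.** The upper boundary is 0.35 + 1.960·0.0754 = 0.498, or 19.9 patients, so it rejects from 20 of 40. By enumeration the upper-tail error is 3.6% and the two-sided size 6.7%, above the nominal 5%.

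**5. Dependence on evaluable patients.** Equal-tailed exact power:

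| Evaluable | 34 | 35 | 36 | 37 | 38 | 39 | 40 |
|---|---|---|---|---|---|---|---|
| Power | 84.5% | 80.7% | 85.4% | 81.8% | 86.2% | 82.9% | 87.0% |

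Section 2 expects adequate bilateral NAF from 77% of women at increased risk. Applying that to this cohort is an assumption: 0.77 × 40 = 30.8, about 31. At 31 the exact rule is 17 or more, with power 78.1%. The normal approximation gives Φ{[0.25 − 1.960·0.0857]/0.0880} = Φ(0.933) = 82.5%.

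**The case against.** **Only a label is wrong.** If the one-sample reading is right, the power statement is true and 40 does not change. Section 3.2 makes feasibility the primary endpoint, so the 35% hypothesis is not the formal primary. All of this stands and limits the weight of the point. It does not make the named test give the stated power, and section 7.2 repeats the two-sample label instead of correcting it.

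**The one-sample origin is an inference.** This is true, since no formula is shown. The alternative is a paired comparison of 35% with 60% across the two breasts. With 40 pairs, McNemar's test has about 85% power at a discordant share of 0.30 and 78% at 0.35, crossing 80% near 0.34. The documents give no discordance, name no paired test, and define the outcome per patient. The one-sample reading fits better, and the failure of the named test does not depend on it.

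**The shortfall at 31 is partly discreteness.** This is fair. Exact power is saw-toothed here: 78.1% at 31, 73.2% at 32, 79.4% at 33. Under the normal approximation the claim survives at 31. Both values should be shown.

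**Stronger readings a reader might infer.**
- *The trial is underpowered, or needs 62 per group.* The documents do not support this, because there is no second group to recruit.
- *Evaluability will be far below 31, because the earlier cohort gave NAF in 13 of 40 patients and analysable miR in 8.* That cohort had no oxytocin, and section 2 attributes the problem to inadequate volumes. The 77% already refers to volume adequate for analysis, so applying the earlier loss on top of it is not justified.

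**A remaining gap.** Section 7.1 does not define altered expression for one pair of breasts across 800 miRNAs. Any restated test inherits that gap, and this point does not resolve it.

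**Conclusion.** The point holds as an error in the named test. Section 7.1's power does not follow from a two-sample z-test: about 61% (64% unpooled) at 40 per group against a stated figure above 80%, a shortfall of at least 16 points on the more favourable of these two versions. A one-sample test against 35% does support the claim, with 87% exact or 91% by approximation. That result assumes 40 evaluable patients, true rates of 35% and 60%, and that a patient-level response can be determined. The sample size is not shown to be too small. The claim holds exactly down to 34 evaluable patients, and at 31 it is borderline and depends on the method. This should be fixed, but it does not call the design into question.

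**What to change.** - **Section 7.1:** replace the two-sample z-test with a two-sided one-sample test of the proportion of patients with altered expression against 35%. Restate the power as 87% at 40 evaluable (exact binomial, 0.025 per tail, 21 or more of 40). If the z approximation is kept, state 91% and disclose the true two-sided size of 6.7%.
- **Section 7.1, one added sentence:** power depends on the number of patients with usable samples from both breasts. Exact equal-tailed power stays above 80% from 34 to 40. At 31, labelled as the 77% yield applied to 40, it is 78% exact or 82% by approximation.
- **Section 7.2:** say that the one-sample test applies to the 35% benchmark, separately from the per-miRNA tumor-versus-normal comparisons, and explain how it relates to the 30% success rule.
- **Study Summary and section 3.1:** reconcile the binomial test against a normative population, and the statement that no power is given, with section 7.1.

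The cost is text changes in four places and no added patients. The exact version also writes an explicit cut-off into the plan, which it does not now contain. The downside is that the stated power becomes conditional on evaluability and may fall slightly below 80% at the expected yield.
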